APPENDIX 6. MANAGEMENT OF DIARRHEA

Episodes of diarrhea have occurred in subjects receiving MEK inhibitors (ie, trametinib [Mekinist USPI] and cobimetinib [Cotellic USPI]) and ERK inhibitors (ulixertinib and GDC-0994) (Adjei et al, 2017; Sullivan et al 2018; Li et al presentation 2017; Varga et al 2020; Infante et al abstract 2015; Infante et al presentation 2015; Welsh and Corrie 2015).

Suggested guidelines regarding management and criteria for adjusting, withholding, and discontinuing study treatment for diarrhea considered to be related to study treatment are provided in Table 17. The institutional standards for the management of GI AEs can differ from these guidelines. In this case, best clinical judgment should be applied.

CTCAE Grade	Management	Action and Dose Modification
Uncomplicated ^a Grade 1 or 2	 Diet: stop lactose-containing products; BRAT diet recommended. Hydration: 8 to 10 large glasses per day. Loperamide^b: Initially 4 mg followed by 2 mg every four hours; maximum 16 mg/day. Continue until diarrhea-free for 12 hours. Diarrhea >24 hours: loperamide every 2 hours, maximum 16 mg/day. Consider adding oral antibiotics. Diarrhea >48 hours: loperamide every 2 hours; maximum 16 mg/day. Consider second-line therapies (budesonide, tincture of opium, or octreotide) and oral antibiotics. Rule out other causes (eg, infection). 	 Continue study treatment. If diarrhea is Grade 2 for >48 hours, interrupt study treatment until diarrhea resolves to ≤Grade 1.° Resume study treatment at the same dose level.
Uncomplicated ^a Grade 3	 Diet: stop lactose-containing products; BRAT diet recommended. Hydration: 8 to 10 large glasses per day. Loperamide^b: Initially 4 mg followed by 2 mg every four hours; maximum 16 mg/day. Continue until diarrhea-free for 12 hours. Second-line therapies and antibiotics if clinically indicated. Hydration: IV fluids if clinically indicated. Rule out other causes (eg, infection). 	 Inform the Sponsor's medical monitor Interrupt study treatment until diarrhea resolves to ≤G1.^c Resume with study treatment at a lower dose level.^c
Grade 4 Any complicated ^d diarrhea	 Urgent intervention indicated. Intervention may require hospitalization for subjects at risk of life-threatening complications. 	 Inform the Sponsor's medical monitor. Permanently discontinue study treatment and report as an SAE.

 Table 17:
 Suggested Management and Dose Modification for Diarrhea

BRAT=bananas, rice, applesauce, toast; CTCAE=Common Terminology Criteria for Adverse Events; IV=intravenous; SAE=serious adverse event.

^a Uncomplicated diarrhea defined by the absence of symptoms.

^b Loperamide should be made available before study treatment so that administration can start at the first signs of diarrhea.

^c Approval of the Sponsor's medical monitor is required to restart study treatment after ≥21 days interruption

^d Complicated diarrhea defined by the presence of symptoms such as pyrexia, sepsis, neutropenia ≥Grade 3, frank bleeding, and/or dehydration requiring IV fluid substitution.

^e Escalation of study treatment to previous dose level may be allowed after consultation with the Sponsor's medical monitor and in the absence of another episode of complicated or severe diarrhea in the 4 weeks subsequent to dose reduction.

APPENDIX 7. LIVER STATUS MONITORING AND MANAGEMENT OF POTENTIAL LIVER INJURY

Liver enzyme elevation has been observed in patients receiving ERK inhibitors (Sullivan et al 2018; Li et al presentation 2017; Varga et al 2020; Infante et al abstract 2015; Infante et al presentation 2015). Clinical symptoms and laboratory test values that are potential signals of liver injury must be regularly reviewed by investigators and by the Sponsor's medical monitor for the study.

Discontinuation of study treatment should occur if a subject shows potential signals of liver injury, indicated by the occurrence of any of the following liver function test values. (Note: liver toxicity or injury may be confirmed with a liver biopsy, if clinically indicated.)

- ALT or AST $\geq 8 \times ULN$.
- ALT or AST >5×ULN but <8×ULN for \geq 7 days.
- ALT or AST >3×ULN and either total bilirubin >2×ULN or INR >1.5, if INR measured.
- ALT or AST >3×ULN with clinical indications of liver toxicity (signs, symptoms, or other diagnostic findings).
- ALT or AST >5×ULN but <8×ULN and subject cannot be closely monitored as described below.

Subjects with potential signals of liver injury must be closely monitored as described below:

- Report the event to the Sponsor's medical monitor.
- Repeat liver enzymes, total bilirubin, and INR at least twice weekly until liver function test elevations resolve or stabilize or the values return to baseline. (The frequency of retesting can decrease to once a week or less if abnormalities stabilize and the subject is asymptomatic.)
- Obtain a detailed history of symptoms, including any prior and concurrent diseases.
- Obtain a history of concomitant drug use (including nonprescription medications and herbal and dietary supplement preparations), alcohol and recreational drug use, and any special diets consumed.
- Rule out acute viral hepatitis (types A, B, C, D, and E), autoimmune or alcoholic hepatitis, nonalcoholic steatohepatitis, hypoxic/ischemic hepatopathy, and biliary tract disease.
- Obtain a history of exposure to environmental chemical agents.
- Review additional tests to evaluate liver status, as appropriate. If alkaline phosphatase (ALP) is elevated, perform an analysis of ALP isoenzymes to determine if the origin of the ALP elevation is bone or liver.
- Consider scheduling the subject for gastroenterology or hepatology consultation.
- Collect ad hoc PK samples.

Subjects who experience ALT or AST values $>3 \times$ to $<5 \times$ ULN, with total bilirubin $<2 \times$ ULN and INR <1.5 (and have no clinical symptoms indicative of liver toxicity) may continue to receive study drug. However, ALT, AST, and total bilirubin tests should be repeated twice weekly until liver function test elevations resolve or stabilize or the values return to baseline. These repeat results will be discussed with the Sponsor's medical monitor. If, at any time, the subject meets any of the above stopping criteria for potential liver injury, study drug treatment should be discontinued and the subject should be monitored as described above.

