7.4. Definition of Dose-Limiting Toxicities

Dose-limiting toxicities are AEs (graded by National Cancer Institute (NCI) Common Terminology Criteria for Adverse Events (CTCAE) v4.03 criteria [Appendix 2]) that occur during the first cycle of treatment and represent any 1 of the following, unless there is a clear alternative cause of the event (eg, disease progression, disease-related):

- Grade 4 thrombocytopenia of any duration.
- Erade 3 hematologic toxicity with complications (eg, Grade 3 thrombocytopenia with bleeding or transfusion requirement).
- Febrile neutropenia of any duration or Grade 4 neutropenia of 5 days or more duration.
- Liver-associated abnormalities defined as:
 - – ≥Grade 3 bilirubin, ALT, or AST elevation, except ALT or AST elevation
 >5×ULN and <8×ULN for <7 days.

 - ALT or AST >3×ULN AND either total bilirubin >2×ULN OR international normalized ratio (INR) >1.5.
 - ALT or AST >3×ULN with clinical indications of liver toxicity (signs, symptoms, or other diagnostic findings).
- \geq Grade 2 eye disorders (ocular toxicities) that do not improve to \leq Grade 1 within 7 days despite treatment discontinuation or documented RVO.
- Symptomatic Grade 2 cutaneous toxicities (including skin rash) that do not improve to ≤Grade 1 within 7 days despite supportive treatment and treatment discontinuation.
- Any other ≥Grade 3 nonhematologic AE except Grade 3 nausea, vomiting, or diarrhea that resolves to ≤Grade 1 by symptomatic treatment within 24 hours.
- Any event that, in the opinion of the DSRC, would suggest that further dose escalation would put subjects at unacceptable risk.

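### Appendix 7 makes INR <1.5 a condition for continued dosing at ALT/AST >3× to <5×ULN, but the twice-weekly repeats it orders for these subjects leave INR out

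*Protocol*

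**What the plan says.** The last paragraph of Protocol Appendix 7 covers subjects with ALT or AST >3× to <5×ULN. Those with total bilirubin below 2×ULN "and INR <1.5 (and have no clinical symptoms indicative of liver toxicity) may continue to receive study drug". For these subjects it orders the following: "However, ALT, AST, and total bilirubin tests should be repeated twice weekly until liver function test elevations resolve or stabilize". It adds a review step, "These repeat results will be discussed with the Sponsor's medical monitor", and a stopping rule: "If, at any time, the subject meets any of the above stopping criteria for potential liver injury, study drug treatment should be discontinued".

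The stopping criteria come earlier in the appendix. The relevant one reads "ALT or AST >3×ULN and either total bilirubin >2×ULN or INR >1.5, if INR measured". The appendix also sets out a close-monitoring panel, which begins "Repeat liver enzymes, total bilirubin, and INR at least twice weekly".

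Section 7.4 uses the same combination in the DLT definition. Its text starts "ALT or AST >3×ULN AND either total bilirubin >2×ULN OR international" and goes on to an INR above 1.5, with no qualifier about whether INR was measured. Section 7.5 withholds dosing in later cycles for toxicity that would have been a DLT in Cycle 1.

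Outside Appendix 7, Table 11 (footnote n) schedules PTT and prothrombin time (or INR) at screening, before dosing on Day 1 of each cycle, and at treatment termination. Sections 9.4.11.2, 9.4.11.4, 9.4.11.6 and 9.4.11.7 order hematology and chemistry, but no coagulation, on Days 8 and 15 of Cycles 1 and 2. Section 9.4.12 leaves assessments after Cycle 6 to the investigator, and its stated minimum does not include coagulation. Table 13 puts coagulation in the extension on a schedule of no less than once every three cycles.

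**The concern.** The rule has two laboratory conditions for continuing besides the transaminase range: bilirubin and INR. The repeat panel tests the first and not the second. A site that follows the panel exactly cannot see, between scheduled coagulation draws, whether the INR condition still holds or whether the INR stopping criterion has been reached. The step meant to catch problems, discussion with the medical monitor, concerns those same repeat results, which contain no INR.

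At stake is the safety of a subject on treatment with a mild transaminase rise whose INR climbs while bilirubin stays below 2×ULN and no symptoms appear. Section 8 lists liver enzyme elevation among the effects that may occur with ASTX029, so subjects in this range are foreseeable.

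**Working it through.** The plan states no figure for this point, so the check compares the texts and then counts days on the schedule.

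**Text comparison, Appendix 7**

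- Conditions for continuing: bilirubin <2×ULN, INR <1.5, no symptoms.
- Repeats ordered for those who continue: ALT, AST, total bilirubin.
- Repeats in the close-monitoring panel: liver enzymes, total bilirubin, INR.
- Stopping criteria that apply at any time: they include ALT/AST >3×ULN with INR >1.5, if INR was measured.

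INR is in the condition, in the stopping criterion and in the parallel panel. It is missing only from the panel for subjects still being dosed at 3–5×ULN.

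**Scheduled coagulation as a substitute** (21-day cycles, coagulation on Day 1)

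- Rise first seen on Day 1: coagulation is drawn at the same visit, and the next scheduled draw is 21 days later.
- Rise first seen on Day 8 of Cycle 1 or 2: the last scheduled draw was 8 − 1 = 7 days earlier, and the next is 22 − 8 = 14 days later.
- Rise first seen on Day 15 of Cycle 1 or 2: the last was 15 − 1 = 14 days earlier, and the next is 22 − 15 = 7 days later.
- After Cycle 6: no interval is fixed until treatment termination.
- Extension: up to 3 × 21 = 63 days between draws.

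For a rise first seen on Day 8 or 15, the INR <1.5 that permits continued dosing could therefore rest on a value one or two weeks old unless a new one is taken. Footnote n also accepts a prothrombin time in place of an INR.

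**Repeat panels in the gap, as upper bounds**

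Taking twice weekly as every 3.5 days, and assuming that the elevation neither resolves nor stabilizes before the next scheduled draw:

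- Day 1 to next Day 1: 21 / 3.5 = 6 repeats, of which 5 precede the scheduled draw.
- From Day 8: 14 / 3.5 = 4 repeats, 3 before it.
- From Day 15: 7 / 3.5 = 2 repeats, 1 before it.

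The repeats end once values resolve or stabilize, so actual counts would often be lower. The intervals in days are the firmer description.

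**The case against.** The appendix can be read as tiered on purpose. One stopping criterion applies to subjects >5× to <8×ULN who cannot be closely monitored. It follows that subjects in that range for less than 7 days may continue under the close-monitoring panel, INR included. On this reading, asymptomatic subjects at 3–5×ULN get a lighter panel by design. So it would be wrong to infer that the INR panel starts only after a stopping criterion has been met. The tiered reading still does not explain why the lighter panel omits a test on which its own permission to continue depends.

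A reader might also infer that INR is absent in every cycle, or that the protocol demands a stop whenever INR exceeds 1.5. Neither is supported. Prothrombin time (or INR) is scheduled on Day 1 of each cycle, with discretion only after Cycle 6. The Appendix 7 criterion needs ALT/AST >3×ULN as well, and applies where INR has been measured. Nor is the unqualified wording in Section 7.4 a real conflict with that qualifier, since an INR that was never taken can meet neither rule.

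There are safeguards. Section 9.4.9 tells sites to test more often when clinically indicated. Section 5.4.5 has extension investigators do whatever standard tests are needed. Section 7.5 calls the appendix criteria suggestions and defers to clinical judgment. Appendix 7 requires regular review of liver signals by the investigators and the medical monitor. Bilirubin, transaminases and symptoms can each still trigger a stop. A careful investigator would probably also read the INR <1.5 condition as calling for an INR. All of this reduces the gap. None of it orders an INR for an asymptomatic subject at 3–5×ULN.

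Finally, a reader might infer that missed INRs led to missed DLTs and so to a wrong dose. The documents give no support for that: they report no frequency of such rises, and Section 7.3 records that the RP2D has been determined.

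**Conclusion.** The point holds as a narrow inconsistency within Appendix 7. Its INR condition and INR stopping criterion cannot be applied from the tests it orders for subjects at ALT/AST >3× to <5×ULN. Between scheduled coagulation draws, INR may go unchecked for up to 21 days in Cycles 1 to 6 and up to 63 days in the extension, with no set interval after Cycle 6. These are upper limits. They assume that no extra test is taken on clinical grounds and that the elevation persists without stabilizing.

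The documents give no frequency for rises of 3–5×ULN, or for a raised INR with bilirubin <2×ULN and no symptoms. The number of subjects affected is therefore unknown and probably small. Endpoints, dose selection and the statistical analysis are unaffected. It is worth correcting because it concerns subject safety and the correction is simple.

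**What to change.** In the last paragraph of Appendix 7:

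1. Add INR to the twice-weekly repeats, so that the panel matches the close-monitoring list.
2. Require an INR with the same draw, or at the first repeat, when ALT or AST first exceeds 3×ULN.

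Leave the thresholds, the routine visit schedule and the qualifier about INR having been measured as they are. Removing the qualifier is not needed once INR is ordered. It could also force a stop in an anticoagulated subject with a mild ALT rise, because the exemption in Section 7.4, "unless there is a clear alternative cause of the event (eg, disease progression, disease-related", belongs to the DLT definition only.

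The cost is a few extra INR tests in the few subjects affected, mostly on blood draws already ordered, and two wording changes in one appendix. Decisions to stop or continue stay with the clinicians.

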APPENDIX 8. DOSE MODIFICATION FOR DECREASE IN LEFT VENTRICULAR EJECTION FRACTION

Decreases of LVEF have been observed in patients receiving the MEK inhibitors trametinib (Mekinist USPI) and cobimetinib (Cotellic USPI) and the ERK inhibitor GDC-0994 (Varga et al 2020). ECHO or MUGA scans will be performed to assess cardiac ejection fraction in regular intervals as outlined in the schedule of events tables (Table 11 and Table 12).

Suggested guidelines regarding management and criteria for adjusting, withholding, and discontinuing study treatment for LVEF decrease are provided in Table 18. In the event that institutional standard practice differs from these suggested guidelines, institutional practices may be followed with best clinical judgement applied.

LVEF Decrease (%)	Action and Dose Modification	
Resting LVEF 49% to 40%; absolute decrease of >10% but <19% in LVEF from baseline and LVEF below the institution's LLN	 Interrupt study treatment and perform ECHO within 3 weeks. If ECHO recovers within 3 weeks: Consult with the Sponsor's medical monitor and request approval to restart ASTX029 dosing. If approval is obtained, restart at a lower dose level. If ASTX029 is restarted, repeat ECHO after 3, 6, and 9 weeks after restart; continue in intervals of every 12 weeks thereafter. If ECHO does not recover within 3 weeks: Consider cardiology consultation. Permanently discontinue study treatment. Repeat ECHO after 3, 6, and 9 weeks or until resolution or 	
Resting LVEF 39% to 20% or >20% absolute reduction from baseline	 plateau. Inform the Sponsor's medical monitor. Permanently discontinue study treatment. 	
Resting LVEF <20%	Consult with a cardiologist.Repeat ECHO after 3, 6, and 9 weeks or until resolution.	

 Table 18:
 Suggested Action and Dose Modification for LVEF Decrease

ECHO=echocardiogram; LVEF=left ventricular ejection fraction; LLN=lower limit of normal.

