5.3. Exclusion Criteria

Subjects meeting any of the following criteria will be excluded from the study:

1. Hypersensitivity to ASTX029 or excipients of the drug product.

- 2. Poor medical risk in the investigator's opinion because of systemic diseases in addition to the cancer under study, for example, uncontrolled infections.
- 3. Life-threatening illness, significant organ system dysfunction, or other condition that, in the investigator's opinion, could compromise subject safety or the integrity of study outcomes or interfere with the absorption or metabolism of ASTX029.
- 4. Prior anticancer treatments or therapies within the indicated time window prior to first dose of study treatment (ASTX029), as follows:
 - a. Cytotoxic chemotherapy or radiotherapy within 3 weeks prior. Palliative radiotherapy to a single lesion within 2 weeks prior. Any encountered treatment-related toxicities (excepting alopecia) not stabilized or resolved to ≤Grade 1.
 - b. Monoclonal antibodies or biologics within 4 weeks prior. Any encountered treatmentrelated toxicities not stabilized or resolved to ≤Grade 1.
 - c. Molecularly targeted drug or other investigational drugs, without the potential for delayed toxicity, within 4 weeks of the first dose of study treatment or 5 half-lives (minimum 14 days), whichever is shorter. Any encountered treatment-related toxicities (excepting alopecia) not stabilized or resolved to ≤Grade 1.
- 5. Prior treatment with ERK inhibitors.
- 6. History of, or at risk for, cardiac disease, as evidenced by 1 or more of the following conditions:
 - a. Abnormal left ventricular ejection fraction (LVEF; <50%) on echocardiogram (ECHO) or multiple-gated acquisition (MUGA) scan.
 - b. Congestive cardiac failure of ≥Grade 3 severity according to New York Heart Association (NYHA) functional classification defined as patients with marked limitation of activity and who are comfortable only at rest.
 - c. Unstable cardiac disease including unstable angina or hypertension as defined by the need for overnight hospital admission within the last 3 months (90 days).
 - d. History or evidence of long QT interval corrected for heart rate (QTc), ventricular arrhythmias including ventricular bigeminy, complete left bundle branch block, clinically significant bradyarrhythmias such as sick sinus syndrome, second- and third-degree atrioventricular (AV) block, presence of cardiac pacemaker or defibrillator, or other significant arrhythmias.

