7.7. Overdose Instructions

Record the actual dose of study drug administered in the source document and on the Dosing eCRF. Record any adverse clinical signs and symptoms associated with a potential overdose on the AE eCRFs. Report signs and symptoms of a potential overdose that meet SAE criteria

(defined in Section 10.1.2) to the Sponsor's Pharmacovigilance group or its designee within 24 hours from the time the investigator first becomes aware of the SAE (see Section 10.2.4). Treat any AE (including SAE) based on standard care for the specific signs and symptoms.

8. **RISKS/PRECAUTIONS**

Refer to the ASTX029 IB for the most current risks and precautions, as well as a list of potential AEs associated with ASTX029 therapy based on nonclinical toxicology studies and clinical findings with other investigational agents in this drug class.

This study represents the first use of ASTX029 in humans, and as with any investigational medicinal product (IMP), subjects may experience reactions or complications that are unknown and therefore unpredictable. Risks to subjects participating in this first evaluation of ASTX029 in a human clinical trial include the potential for adverse reactions.

Based on nonclinical toxicology studies with this molecule, and clinical findings with other investigational agents in this drug class (ERK inhibitors; ie, ulixertinib and GDC-0994) (Sullivan et al 2018; Li et al presentation 2017; Varga et al 2020; Infante et al abstract 2015; Infante et al presentation 2015), the ASTX029 mechanism of action may result in cutaneous AEs (eg, rash, pruritus, dry skin), GI AEs (eg, diarrhea, nausea, vomiting, and esophagitis), fatigue, peripheral and periorbital edema, LVEF decrease, potential arrhythmias, visual disturbances, and liver enzyme elevation.

The potential for these AEs warrants frequent monitoring of subjects participating in clinical trials of ASTX029 until the safety profile is further understood. In particular, clinical signs and/or symptoms of cutaneous, ocular, GI, and liver toxicities and LVEF decrease will be closely monitored, evaluated, and managed during the study (Appendix 4, Appendix 5, Appendix 6, Appendix 7, and Appendix 8 respectively).

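### The row limits in Table 18 (LVEF decrease) do not meet: if every part of row 1 must hold, a fall of 20 points (or 19, as printed) to LVEF 40-49% belongs to no row.

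*Protocol*

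**What the plan says.** Table 18 in Protocol Appendix 8 sorts subjects by resting LVEF and by absolute fall from baseline.

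- **Row 1:** "Resting LVEF 49% to 40%; absolute decrease of >10% but <19% in LVEF from baseline and LVEF below the institution's LLN". The first step is "Interrupt study treatment and perform ECHO within 3 weeks". If the ECHO recovers within 3 weeks, the medical monitor is consulted: "If approval is obtained, restart at a lower dose level". Without recovery in that time, treatment stops permanently.
- **Row 2:** "Resting LVEF 39% to 20% or >20% absolute reduction from baseline". The action is "Permanently discontinue study treatment", with no recovery branch.
- **Row 3:** an LVEF below 20%. In the text available it appears to share row 2's action cell.

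Appendix 8 describes these as suggestions and lets a site follow its own standard practice where that differs. It has no rule for a subject who meets two rows or none. Section 7.5 refers LVEF decrease to this appendix. At entry, exclusion criterion 6a removes subjects with "Abnormal left ventricular ejection fraction (LVEF; <50%) on echocardiogram (ECHO"), so baseline is at least 50%. Section 8 names LVEF decrease among the risks to be followed: "GI, and liver toxicities and LVEF decrease will be closely monitored, evaluated, and managed during the study".

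**The concern.** Row 1 ends below a 19-point fall and row 2 begins above a 20-point fall, so falls from 19 to 20 points can drop between them. Row 1 also joins its LVEF range to its fall limits with a semicolon, whereas row 2 uses an explicit 'or'. A site therefore has to decide for itself whether the range and the fall limits are joint conditions or alternatives.

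LVEF decrease is a named risk, and this is the only place in the protocol that gives LVEF thresholds for action during treatment; the list of dose-limiting toxicities in Section 7.4 has none. A subject in no row gets no Table 18 instruction to interrupt or to repeat the scan. After the first 4 cycles, Section 9.4.5 schedules ECHO or MUGA every 4 cycles, which is 4 × 21 = 84 days.

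The data consequence is smaller. SAP 7.6.10 plans no particular analysis of ECHO/MUGA, so planned outputs would not show inconsistent handling directly. It could still enter the summaries of interruptions and of discontinuations due to adverse events in SAP 7.6.1 and 7.6.2.

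**Working it through.** The plan has no figure to reproduce; the check is whether the rows place each subject once.

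**Inputs.** Row limits are from Table 18. Baseline is at least 50% (Section 5.3, criterion 6a). Let B be baseline, V the on-study LVEF and D = B − V, in whole percentage points. Two quantities are assumptions, because the documents do not give them: the highest baseline (75% or 80%) and the institutional lower limit of normal, LLN (tried at 50%, 52% and 55%).

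**Reading A: all parts of row 1 must hold.**
Row 1: 40 ≤ V ≤ 49, and 10 < D < 19, and V below LLN.
Row 2: 20 ≤ V ≤ 39, or D > 20.

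| Baseline | On study | Fall | Row |
|---|---|---|---|
| 60% | 42% | 18 | 1 |
| 60% | 41% | 19 | none |
| 60% | 40% | 20 | none |
| 61% | 40% | 21 | 2 |

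Unassigned pairs with V from 40 to 49 and D of 19 or 20: 10 values × 2 falls = 20, with baselines from 59% to 69%. They fail row 1 on the size of the fall, so the LLN and the cap on baseline do not affect them.

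Falls of 10 points or less to 40-49% also meet no row: 1 + 2 + … + 10 = 55 pairs, from 50→40 up to 59→49. These lie below the lower limit of row 1, not between two action bands.

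**Sensitivity to the printed sign.** If the limit in row 1 were ≤19% instead of <19%, a fall of 19 would move into row 1. A fall of exactly 20 still fails both D ≤ 19 and D > 20, so 10 of the 20 pairs would remain unassigned.

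**Reading B: LVEF 40-49% is enough alone.** The 20 pairs now fall in row 1. Every fall of more than 20 points to 40-49%, however, meets rows 1 and 2 together:

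- Baseline capped at 80%: 20 + 19 + … + 11 = 155 pairs.
- Baseline capped at 75%: 15 + 14 + … + 6 = 105 pairs.

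Examples are 61→40 and 65→42. If the fall limits with LVEF below LLN are likewise enough without the range, falls of 11 to 18 points to below 40% also meet both rows: 8 + 7 + … + 1 = 36 pairs, for example 50→32.

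The results for LVEF 40-49% were the same at all three LLN values. Neither reading gives exactly one row for every fall to 40-49%.

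**The case against.** The strongest reply is that Table 18 is guidance and not the only safeguard. Sections 7.1.4 and 7.5 allow dosing to be reduced, withheld or stopped for unacceptable treatment-related toxicity. Section 9.4.5 requires a clinically significant ECHO/MUGA finding after treatment starts to be recorded as an adverse event. A reader might infer that a subject with a 20-point fall gets no action and stays on full dose; the documents do not support that, since only Table 18 is silent. Whether the withholding rule in Section 7.5 would be triggered depends on how CTCAE v4.03 grades such a fall, which the documents do not reproduce.

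A reader might also infer that Reading B gives two opposite instructions. It does not. Both rows stop dosing at once, and row 1 also ends in permanent discontinuation if there is no recovery within 3 weeks. They part only for a subject who recovers in time and whose restart the medical monitor approves. Reading B is also the weaker one: it leaves the 19% limit with no effect for subjects at 40-49%, and the drafter wrote 'or' in row 2 where alternatives were meant.

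Three further cautions are fair. The pair counts are not expected numbers of subjects, because no LVEF distribution is given. The 55 small falls may simply lie below the intended threshold for action. Falls of 19 or 20 points to 50% or above but below LLN can be called unassigned only if an institution's LLN exceeds 50%, which the documents do not state. The semicolon or the sign before 19% may also have been altered when the table was read from PDF.

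What survives is the boundary itself. The clause on institutional practice does not tell a site that uses the table which row applies, and a fall of exactly 20 points stays unassigned under Reading A with either sign.

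**Conclusion.** The point holds as an inconsistency between the limits of rows 1 and 2. Under the more natural reading, falls of 19 and 20 points to LVEF 40-49% (20 whole-number pairs) have no row, although falls of 18 and 21 points do. Only the 20-point half is independent of the printed sign. Under the weaker reading the gap closes, but falls of more than 20 points to 40-49% meet two rows that differ on restart, without a rule of precedence.

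This should be fixed but is not a must-fix: the gap is narrow, the table is suggested guidance, general toxicity rules remain, and no effect on the primary endpoints is shown. The conclusion rests on the current table text and the entry limit of 50%. The assumed cap on baseline affects only the overlap counts.

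**What to change.** The sponsor should check the punctuation and signs against the source table, then reconcile the rows of Table 18: replace the semicolon in row 1 with an explicit AND or OR, make the limits of rows 1 and 2 meet, and state which row governs if two apply. It would help to say whether falls of 10 points or less to 40-49% are meant to be outside the table. Which action covers the unassigned falls is for the sponsor's medical monitor and the DSRC to decide; no clinical rule is proposed here.

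The cost is a wording change to one table, with no new assessments or subjects. Section 14.4 allows an administrative letter to correct obvious inconsistencies. If assigning an action to the unassigned falls is judged a substantive change, it belongs in the next amendment.
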